3.1. Recruitment

Participants will be recruited from two sites: Wake Forest School of Medicine (Site Pl: [name]) and the University of Pennsylvania (Site PI: [name]). Participants will be recruited through flyers, direct mailings, television, radio, newspaper, bus, social media, online via our recruitment website, the CTSI Registry, and Craigslist advertisements that read, "If you smoke, we could use your help. If you're (age 18-24 or 25 or older), smoke and have tried e-cigarettes or vaping multiple times, you may be eligible for a 4 month study on tobacco use—during which you will be paid for your time and effort. This is NOT intended as a treatment for smoking." Additional ads will be run as needed targeting smokers who would fit under-enrolled age categories. These ads will be identical but specify the age range ("age 18-24..." "age 25 or older..."). Individuals who are interested will leave their contact information on a voicemail, or enter it on a form on our website. Research staff will call each participant and read a script briefly explaining the study. After verbal informed consent is received, the participants will be asked questions over the phone to determine initial eligibility. If eligible and interested, they will be scheduled for an informational session during which they will be provided with a copy of the consent document and shown a PowerPoint presentation that outlines the procedures, benefits/risks, compensation and the participants' rights. They will also be able to ask questions about the study. They will receive \$10 in transportation costs for the informational session. If they are still interested in participation, then they will be scheduled for an in-person screening visit. Potential participants will be instructed to bring a pack of their usual brand cigarettes, all prescription medications they are currently taking, and a valid, state-issued photo ID to the screening visit. Acceptable forms of identification include a Driver's License, State Photo ID Card, State Voter ID Card, Passport, or Military ID. If the potential participant does not have a valid, state issued photo ID, the interviewer can provide him/her with information on obtaining one. Participants will be given the option to receive study information and visit reminders by phone, email, and text message.

A participant must complete his/her in-person screening session within 30 days of completing the telephone recruitment questionnaire. If the participant is not able to attend the in-person screening visit in that timeframe, he/she will need to complete the telephone recruitment questionnaire again and will be given a new REDCap ID number.

3.2. Informed Consent Process

Before beginning the informed consent process, participants will need to produce valid, state issued photo identification. The interviewer will confirm the age and identity of the participant. If the participant is not age 18 or older, he/she will be dismissed without payment. During the in-person screening session, study information will be presented and written, informed consent will be required to participate in the screening. To ensure adequate informed consent, participants will be asked to read the first several lines aloud (to determine literacy) and will then be given ample time to read the consent document. If the interviewer determines that the participant is not literate, he/she will dismiss the person from the study. The interviewer will review the PowerPoint presentation if necessary. The participant will be instructed to read several open-ended questions aloud and

discuss the answers with the researcher. Only after the participant and the researcher are fully satisfied that the participant understands the purpose of the study, the confidentiality of the data, the procedures, the risks/benefits and his/her rights as a research participant will the consent form be signed and the participant undergo screening procedures.

3.3. Screening Procedures

Physiological measures collected and recorded on paper, and entered into REDCap by the interviewer at the end of the visit:

- 1. Breath alcohol concentration (BrAC)
- 2. Expired breath carbon monoxide (CO).
- 3. Urinary cotinine strips, if needed
- 4. A urine toxicological screen
- 5. Weight and height
- 6. Pregnancy Tests (HCG detection)
- 7. Blood pressure and heart rate

Screening questionnaires administered on paper and entered into the study databases at the end of the visit:

- 1. Identifying Information Form
- 2. Brief Medical History Questionnaire
- 3. Prime MD

Screening assessments administered via interview and entered into REDCap by the interviewer:

- 1. Concomitant Medications Form
- 2. The Mini International Neuropsychiatric Interview (MINI) suicide subscale
- 3. Tobacco Use History Questionnaire
- 4. Smoking Cessation Therapy Use Questionnaire
- 5. Drug Use Questionnaire (12 month and 1 month version)

Assessments administered on paper and kept as a source document only:

- 1. Brief Medical History Follow-Up Questionnaire, if needed
- 2. BDI, if needed
- 3. GAD 2 week monitoring, if needed

Screening assessments administered directly via Redcap:

- 1. Demographic Questionnaire
- 2. Center for Epidemiological Studies-Depression Scale
- 3. Alcohol Use Questionnaire (12 month and 1 month version)
- 4. Smoking Stages of Change

If the Redcap website is not functioning, the assessments will be printed out and administered on paper. The source documents will be kept in the participant's binder. The interviewer will enter the data into Redcap when it resumes functioning properly. This information should be recorded in the 'End of Visit Evaluation Form' and entered in to REDCap.

The following task will be completed after initial eligibility determination by the research assistant (prior to review by medical staff):

1. Puff topography entails having participants smoke through a device that more precisely measures puffing behavior (e.g., puff volume). At screening, participants will smoke a usual brand cigarette through the topography device.

3.4. Eligibility Determination

Research staff will determine initial eligibility after reviewing all eligibility criteria except for the medical/psychiatric history. If the participant is deemed eligible, he/she will complete the puff topography assessment, be trained on using the IVR system (see Section 9), and be scheduled to come in for the baseline visit. Participants will be instructed to use tobacco products as usual between the screening visit and the baseline visit.

Final eligibility of the participant will be determined by a licensed medical monitor (LMM) after reviewing the Brief Medical History Questionnaire, Medical History Follow-Up Questionnaire and the MINI suicide subscale. If the participant's score on the Prime MD indicates a psychiatric disorder, then the Prime MD will be submitted to the licensed medical monitor for review as well. Additionally, if the participant's score on the Prime MD indicates Major Depressive Disorder, then the Prime MD along with the Beck Depression Inventory will be submitted for review. The LMM will sign off prior to the Baseline Visit that the participant is medically stable to receive the study product(s). The LMM will not review the medical history forms of participants who are not eligible for other, non-medical reasons.

Once all the screening procedures have been completed, researchers will pay ineligible participants \$30 for their time as long as they pass the drug and breathe alcohol tests and meet the minimum requirements for carbon monoxide or urinary cotinine levels. Those participants who do not pass these tests or meet these requirements will be dismissed from the study without payment. If a participant does not pass the drug test but has a current, valid prescription that would explain the failed test, then he/she will not be automatically excluded and will still receive \$30.

At the end of the Screening/Baseline Visit, the researcher will complete the End of Visit Evaluation Form, which will be entered into REDCap. This will allow the researcher to make note of any

problems encountered during the visit and to assess the truthfulness of the participant regarding self-report of tobacco use.

3.5. Inclusion Criteria:

- 1. Age 18+
- 2. Daily smokers who smoke an average of at least five and 50 or fewer cigarettes per day for the last month.
- 3. Must have used a vaping device on 2 or more separate occasions before participating in the trial
- 4. Expired breath carbon monoxide (CO) level to assess recent smoking. Carbon monoxide level must be ≥ 10 ppm to confirm regular daily smoking. If CO is <10 ppm, NicAlert strips will be used to assess urinary cotinine quantity to confirm smoking status. A result of 2,000 ng/mL is needed to verify regular daily smoking.

3.6. Exclusion Criteria:

- 1. Unwilling to use research cigarettes or a vaping device as part of the trial
- 2. Currently trying to quit or intending to quit smoking in the next 60 days
- 3. Currently seeking treatment for smoking cessation
- 4. A quit attempt in the past 30 days resulting in greater than 3 days of abstinence
- Using tobacco products, including nicotine replacement therapies or other pharmacotherapies (other than cigarettes, vaping devices or roll-your-own tobacco) more than 9 days in the past 30 days
- 6. Roll your own tobacco users that are unwilling to smoke machine manufactured cigarettes as part of the trial
- 7. Use of vaping devices > 15 days of the last 30
- 8. Conditions in which participation is likely to pose a significant threat to health or for which the condition could interfere with the ability of the participant to fully participate
- 9. Significant unstable medical conditions (any significant **change** in a serious medical condition occurring during the past 3 months including cardiovascular disease, COPD, and cancer, as determined by the licensed medical monitor)
- 10. Significant unstable psychiatric conditions (any significant **change** in psychiatric symptoms during the past 3 months as determined by the licensed medical monitor)
- 11. Schizophrenia and schizoaffective disorder
- 12. Positive toxicology screen for any of the following drugs: cocaine, opiates, methadone, benzodiazepines, barbiturates, amphetamines, methamphetamines, and PCP. Positive test for marijuana only allowed. Failing temperature strip for the sample or unable to provide enough urine sample for the drug screen.
 - a. Participants with valid prescriptions for opiates, benzodiazepines, barbiturates, amphetamines or methadone (clinic letter) will not be excluded.
- 13. Self-reported illicit use of any drug including marijuana ≥ 10 days in the past month
- 14. Breath alcohol level > 0.01 (g/dL), as measured by a breath sample.
- 15. Binge drinking alcohol (more than 9 days in the past 30 days, 4/5 drinks in a 2-hour period (female/male))

- 16. Pregnant, trying to become pregnant or breastfeeding
- 17. Failure to agree to use adequate protection to avoid becoming pregnant during the study
- 18. Currently taking any one of the following medications:
 - a. Phenytoin [Brand Name: Dilantin]
 - b. Carbamazepine [Brand Name: Tegretol, Carbatrol, Equetro, Epitol]
 - c. Oxcarbazepine [Brand Name: Trileptal]
 - d. Primidone [Brand Name: Mysoline]
 - e. Phenobarbital
 - f. Bendamustine [Brand Name: Treanda]
 - g. Clopidogrel [Brand Name: Plavix]
 - h. Clozapine [Brand Name: Clozaril, FazaClo]
 - i. Erlotinib [Brand Name: Tarceva]
 - j. Flecainide [Brand Name: Tambocor]
 - k. Fluvoxamine [Brand Name: Luvox]
 - I. Irinotecan [Brand Name: Camptosar]
 - m. Olanzapine [Brand Name: Zyprexa]
 - n. Tacrine [Brand Name: Cognex]
 - o. Theophylline [Brand Name: Theo Dur]
- 19. CO reading >80 ppm
- 20. Systolic BP greater than or equal to 160 mm/Hg
 - a. Participants failing for blood pressure will be allowed to re-screen once.
- 21. Diastolic BP greater than or equal to 100 mm/Hg
 - a. Participants failing for blood pressure will be allowed to re-screen once.
- 22. Systolic BP below 90 mm/Hg
 - a. Participants failing for blood pressure will be allowed to re-screen once.
- 23. Diastolic BP below 50 mm/Hg
 - a. Participants failing for blood pressure will be allowed to re-screen once.
- 24. Heart rate greater than or equal to 105 bpm
 - a. Participants failing for heart rate will be allowed to re-screen once.
- 25. Heart rate lower than 45 bpm
 - a. Participants failing for heart rate will be allowed to re-screen once.
- 26. Indicating any suicidal ideation in the past month or suicide attempts in the past 5 years (if within the past 6-10 years, LMM approval required).
- 27. Inability to independently read and comprehend the consent form and other written study materials and measures.
- 28. Having participated in a research study during the past three months in which the participant:
 - a. Smoked a cigarette that was not his/her usual brand cigarette for more than one day
 - b. Used any tobacco products beyond normal use for more than one day
 - c. Used any nicotine replacement products or smoking cessation medications for more than one day
- 29. Having participated in prior studies involving reduced nicotine cigarettes in the past three years.
- 30. Household member enrolled in the study concurrently
- 31. Self-reported allergies to propylene glycol and/or vegetable glycerin.

32. Previous adverse reactions when using vaping devices.

Children under age 18 are excluded because they cannot legally buy cigarettes. Those with unstable medical or psychiatric conditions are excluded as these symptoms could affect a participant's ability to complete the study. Examples include but are not limited to the following: angina, stroke, heart attack which occurred since phone screening, blood clots in the arms or legs for which the individual is undergoing active medical treatment, cancer requiring active chemotherapy or radiation therapy, severe shortness of breath caused by conditions such as uncontrolled asthma, COPD, or arrhythmia, active untreated infection such as pneumonia, active untreated endocrine disorder such as hyperthyroidism. The LMM can also exclude participants for conditions in which participation is likely to pose a significant threat to health or for which the condition could interfere with the ability of the participant to fully participate (e.g. severe allergic reaction to propylene glycol or vegetable glycerin found in e-liquids). We will exclude those currently seeking smoking treatment, those who have quit smoking for longer than 3 days in the past 30 days or are planning to guit in the next 60 days, as participation in this study may not lead to reductions in smoking. We will exclude pregnant and nursing women and anyone with current or recent alcohol or drug abuse problems as these factors could independently affect smoking behavior during the study. Individuals with baseline CO readings greater than 80 ppm, those with heart rate or blood pressure readings that are out of range and anyone who has attempted suicide in the past five years will be excluded from the study for safety concerns. Participants currently prescribed one of the medications listed will be excluded because this medication could interfere with the biomarkers or possibly cause an adverse smoking-drug interaction if there are changes in smoking behavior. If an individual has recently participated in a smoking research study that changed his/her smoking behavior, this person would be excluded because he/she would not have a stable smoking baseline. Because participants are required to complete portions of the protocol independently both in the lab and at home, they will need to be able to independently read and comprehend the study materials. Multiple participants within the same household may not enroll concurrently to avoid product exchanging. Very frequent use of vaping devices is exclusionary to target individuals who are primarily cigarette smokers and to decrease the likelihood that a participant will have a vaping device they find more satisfying than the study vaping device. However, individuals must have at least tried vaping devices at least on 2 separate occasions, without an allergic or otherwise adverse experience, to maximize the likelihood that participants will try the vaping device provided to them.

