1.3.1. Nicotine

Nicotine delivered via vaping devices may serve a variety of functions that support its actions as a reinforcer and an appealing alternative to smoking VLNC cigarettes. Some vaping devices can deliver as much or more (among experienced users) nicotine as a traditional cigarette with a relatively rapid rate of absorption (Tmax≤5 min) (Spindle, Breland, Karaoghlanian, Shihadeh, & Eissenberg, 2015). In devices similar to the one proposed here, e-liquids with 18-36 mg/ml produce cigarette-like increases in plasma nicotine concentrations after 10 puffs while lower nicotine content e-liquids produce smaller and short-lived increases in plasma nicotine (Lopez et al., 2016; Hiler et al., 2017). This pharmacokinetic profile suggests that vaping devices may have greater positive reinforcing effects than VLNC cigarettes (Ramoa et al., 2016). Vaping devices can also be used throughout the day to maintain nicotine levels that would otherwise fall by 95% or more if smokers use only VLNC cigarettes (Denlinger et al., 2016). Indeed, vaping devices reduce withdrawal symptoms in cigarette smokers (Dawkins, Turner, & Crowe, 2013; Dawkins, Turner, Hasna, & Soar, 2012), and this suppression is dependent on the nicotine concentration of the e-liquid (Dawkins et al., 2012). Relatedly, greater nicotine delivery may also result in increased risk of dependence on vaping devices (Etter & Eissenberg, 2015). Finally, nicotine also acts peripherally on receptors in the oropharyngeal cavity which may contribute to sensory effects (discussed below) that might generalize across products. Together, these data suggest that vaping devices that effectively deliver nicotine may be more likely to function as both positive and negative reinforcers and more able to compete with the reduced reinforcing effects of VLNC cigarettes.

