5.3. Randomization Visit Procedures

Physiological measures collected and recorded on paper, and entered into REDCap at the end of the visit:

- 1. BrAC
- 2. Weight
- 3. CO
- 4. Blood Pressure
- 5. Heart Rate
- 6. Urine Pregnancy Test, if applicable

Biological specimens collected, stored, and entered into CENIC Biosample Collection Platform:

1. First void urine sample for smoking biomarker assessment:

Participants will be asked to bring a urine sample (first void of the day) to the Randomization Visit for biomarker assessment. Samples will be stored at temperatures approximately at -20°C (UPenn) or -80°C (Wake Forest). Urine samples will be sent regularly to be analyzed and stored at the University of Minnesota. We will assess mercapturic acids, and total nicotine equivalents (TNEs). If a participant forgets to bring his/her urine sample, then the spot urine sample will be used.

2. Spot urine sample for assessing baseline anatabine:

Participants will be asked to provide a urine sample in the lab for biomarker assessment. Samples will be stored at temperatures approximately at -20°C (UPenn) or -80°C (Wake Forest). Urine samples will be sent regularly to be analyzed and stored at the University of Minnesota.

Assessments administered via interview and entered into REDCap by the interviewer:

- 1. Concomitant Medications Form
- 2. Adverse Event Form, if applicable
- 3. Health Changes Questionnaire
- 4. IVR Review of Daily Call and follow-up on missing and unusual reports and Timeline Follow-back Questionnaire (since last visit); if needed
- 5. Intention to Quit Smoking and Vaping

Assessments administered on paper and kept as a source document only:

- 1. BDI, if applicable
- 2. GAD 2 week monitoring, if needed

Assessments administered directly via REDCap:

- 1. Respiratory Health Questionnaire
- 2. Cigarette Dependence Measures
- 3. Vaping Device Dependence Measures
- 4. Minnesota Nicotine Withdrawal Scale
- 5. Context of Product Use-Baseline
- 6. Urge to Use Questionnaire-Baseline
- 7. Perceived Health Risks Questionnaire: Study Products

If the Redcap website is not functioning, the assessments will be printed out and administered on paper. The source documents will be kept in the participant's binder. The interviewer will enter the data into Redcap when it resumes functioning properly. This information should be recorded in the 'End of Visit Evaluation Form' and entered in to REDCap.

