Participants will be trained to use the Interactive Voice Response (IVR) System, which will contact participants each day throughout the study and ask about their smoking and vaping behavior. Participants will be provided a study cell phone if they have unreliable telephone access, do not have enough monthly cell phone minutes or prefer not to use their own phone. Each day during the period between the screening visit and the Week 12 Visit the IVR system will ask participants to report their use of cigarettes, puffs of a vaping device, first tobacco product used, and minutes after waking until first tobacco product use. During each call, participants report about tobacco use during the previous calendar day (midnight to midnight), not the previous 24-hours.

The IVR system is operated by MicroAutomation, a media production company. To be enrolled in the IVR system, research staff will enter the participant's telephone number, subject identifier, and visit dates into the IVR CENIC website. Identifying information (telephone numbers) will be removed from the dataset by the biostatistics core. Please refer to MicroAutomation's privacy statement and HIPAA compliance form for additional information.

11. Study Debriefing

After data collection is complete, participants will receive a letter telling them which condition they were randomized into and the results of the study thus far.

12. Biosample Storage

The urine and saliva biosamples will be collected and stored at study sites until regular shipments to the University of Minnesota Masonic Cancer Center for analysis or long term storage. Samples that are not used for primary analysis of study biomarkers will be banked for future use related to tobacco and nicotine exposure.

13. Data Storage

Data will be stored locally at each site and at the University of Minnesota Masonic Cancer Center's Bioinformatics Core for at least 7 years after study completion.

14. Individually Identifiable Health Information

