Our primary objective is to test the main effects of cigarette nicotine content, e-liquid nicotine content and e-liquid flavors, as well as the interactions among these factors. The primary endpoint will be total CPD (i.e. study plus non-study CPD) based on IVR-Revised. The primary analysis will compare CPD by factor at the week 12 visit using linear regression. Treatment groups should be balanced at baseline, and as a result our primary analysis will only adjust for baseline CPD, week and the three stratification factors (site, age, and menthol preference). This will be considered the "unadjusted model" for the purposes of this document. We will start with a model that includes all two-way interactions between the three factors (note: the three way interaction will not be considered). Two-way interactions that are not significant will be removed from the model and the final model will include the three factors, any two-way interactions significant at the 0.05 levels, baseline CPD, and the three stratification factors. The estimation and testing of main effects in the presence of significant interactions will be completed within levels of the other factor, otherwise, global estimates of the main effects will be obtained. Whenever possible, secondary endpoints will be analyzed following the approach to testing the main effects and interactions described above. Biomarkers of toxicant exposure are expected to be skewed and will be analyzed on the log scale. Likewise, exploratory endpoints will be analyzed following the approach outlined above using a linear mixed model or logistic regression, as appropriate, depending on the type of endpoint (continuous, binary). Finally, we will complete subgroup analyses following the approach described above within each subgroup (age: 18 - 24 vs. 25+; menthol preference; sex). We will not use formal multiple comparison adjustments for secondary endpoints because we have included only 2 outcomes that are likely correlated with each other and the primary endpoint. Likewise, we will not correct for multiple comparisons for our subgroup analyses as they are considered exploratory.

Study staff will make every effort to minimize missing data in the proposed clinical trial. The success of our previous and ongoing trials suggests that missing data will be minimal. Nevertheless, we plan to complete a sensitivity analysis to evaluate the impact of missing data on trial conclusions.

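### Pre-randomization vaping is recorded daily but enters no outcome model: lost precision, mainly for the exploratory vaping-use outcomes

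*Combined protocol and SAP*

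**What the plan says.** **Who may enter.** Section 3.5 requires some vaping history: "Must have used a vaping device on 2 or more separate occasions before participating in the trial". Section 3.6 excludes "Use of vaping devices > 15 days of the last 30". One participant may therefore have vaped twice ever and another on half of the last 30 days.

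**What is recorded before randomization.** Section 10 says that "the IVR system will ask participants to report their use of cigarettes, puffs of a vaping device", and that it does so "Each day during the period between the screening visit and the Week 12 Visit". The timeline in section 2.1 puts randomization at day 14 after screening. Section 5.3 also lists "Vaping Device Dependence Measures" at the randomization visit.

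**What is modelled.** Section 29 states that "our primary analysis will only adjust for baseline CPD, week and the three stratification factors", naming site, age and menthol preference as those factors. Secondary endpoints follow the same approach where possible, and exploratory endpoints follow it through linear mixed or logistic models. Section 28.3 places the vaping-use outcomes among the exploratory ones: days using the assigned device, puffs per day, and ml of e-liquid per week. Subgroups are age, menthol preference and sex. Section 29 labels the primary model as unadjusted, but defines no adjusted counterpart.

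**The concern.** Two of the three randomized factors, e-liquid nicotine and e-liquid flavor, reach the participant through the vaping device. How much someone already vaped is an obvious candidate to predict how much they vape during the trial, and perhaps how much they smoke. The plan makes no use of it as a stratum, covariate or subgroup.

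The gap is clearest for vaping use. For CPD, the baseline value of the outcome is in the model. The vaping-use outcomes concern the assigned device, which nobody has before randomization, so they have no baseline value of their own. Recent vaping is the natural substitute, and baseline CPD is a poor one. What is at stake is wider confidence intervals than the collected data require.

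**Working it through.** **Inputs.** Section 30 gives 480 enrolled, 75% retention (360 completers), type I error 0.05, and a CPD difference of 6.3 with SD 7.2. In scenario B the flavor effect is half of that: 6.3 / 2 = 3.15. Section 29 gives equal allocation to eight groups. Assumed here: a two-sided test, and 7.2 as the residual SD of the planned model.

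**Step 1: reproduce the plan's figure.** A two-way interaction collapses the eight groups to four cells of 360 / 4 = 90.

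- SE = 7.2 × √(4/90) = 1.518
- Power = Φ(3.15/1.518 − 1.96) = Φ(0.115) = 0.546

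Section 30 states 0.54 (Interaction B). The other CPD entries agree too: main effect B and Interaction A are both 0.986 against a stated 0.99, and the subgroup interaction is 0.835 against 0.83.

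**Step 2: add a baseline vaping covariate.** With partial correlation r between the covariate and the outcome, residual variance is multiplied by (1 − r²), the SE by √(1 − r²), and the equivalent number of completers is 360 / (1 − r²). The documents give no r, so a range is shown.

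| Assumed r | Residual variance removed | Equivalent completers | CPD Interaction B power |
|---|---|---|---|
| 0 | 0% | 360 | 0.55 |
| 0.1 | 1% | 364 | 0.55 |
| 0.2 | 4% | 375 | 0.56 |
| 0.3 | 9% | 396 | 0.59 |
| 0.4 | 16% | 429 | 0.62 |
| 0.5 | 25% | 480 | 0.67 |

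For CPD, with baseline CPD already in the model, 0.1 to 0.3 is the reasonable part of the table: a gain of 0.00 to 0.04. CPD main effects have about 0.99 power in either case. For vaping use, higher values are more plausible. Section 30 gives no power for those outcomes, so only the variance and equivalent-completers columns apply to them. At r = 0.5 the standard error falls by 1 − √0.75 = 13%.

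**Step 3: does leaving the covariate out cause bias?** A simulation used 360 completers in eight equal groups, 4,000 data sets per setting, and prior vaping drawn uniformly from 0 to 15 days (an assumption).

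| Share of variance due to prior vaping | Mean estimate, covariate omitted (true 3.15) | Type I error, omitted | Power, omitted | Power, included |
|---|---|---|---|---|
| 0.05 | 3.13 | 0.052 | 0.54 | 0.56 |
| 0.10 | 3.13 | 0.048 | 0.53 | 0.58 |
| 0.20 | 3.16 | 0.053 | 0.54 | 0.64 |

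Omission produced no bias and no inflation of type I error. The only cost was power.

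**The case against.** Adjusting for baseline CPD and the strata is a valid pre-specified choice, and no trial adjusts for every prognostic variable. The primary endpoint gains almost nothing at the correlations one would expect for CPD, and the outcomes that could gain more are exploratory. The covariate is also imperfect. It measures a nominal 14 days, although each of the two pre-randomization intervals may run to 21 days (sections 4.1 and 5.1). In the second interval participants hold a free supply of their usual cigarettes. Someone who tried vaping twice and a former heavy vaper who stopped could both score zero. Finally, section 30 does not say whether 7.2 is already adjusted for baseline CPD; if it is not, planned power is above 0.54 and the starting row of the table is too low.

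Most of this stands, and it limits the point to an inexpensive gain in precision. It does not argue for omission. A covariate measured before randomization needs only to predict the outcome, and a percentage of completed calls copes with an uneven window.

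Three stronger readings are tempting and are not supported:

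- *That prior vaping leaves the arms unbalanced and the comparisons biased.* Randomization is not stratified on it, but balances it in expectation; the simulation agrees.
- *That 0.54 is the weakest planned test.* Section 30 lists lower values for the same scenario: 0.41 for FTND and 0.25 for log(CEMA). The 0.54 also applies only if flavor has half the nicotine effect; at equal effects the stated power is 0.99.
- *That the background shows experience changing nicotine delivery from the study device.* Section 1.3.1 says "Some vaping devices can deliver as much or more (among experienced users) nicotine as a traditional cigarette". Its next sentence, on devices like the study device, ties delivery to e-liquid concentration and does not mention experience. Nor does the eligibility rationale in section 3.6 make that claim: it speaks of enrolling people who are mainly cigarette smokers, of avoiding a competing device, and of making it likely that the device is tried.

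**Conclusion.** The point holds as a modest, inexpensive improvement. The plan collects recent vaping before randomization and leaves it out of the models where it is most likely to matter, those for use of the assigned device. The loss is precision: 1% to 25% of residual variance at assumed partial correlations of 0.1 to 0.5, with the upper part plausible only for vaping use. For CPD, Interaction B power of about 0.55 becomes 0.55 to 0.59 at correlations of 0.1 to 0.3, and main effects do not change in practice.

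This rests on the assumed correlations, on 7.2 being the residual SD, and on linear models. It also rests on reading section 29's covariate list as carrying over to the exploratory outcomes. The text says that they follow the approach, but gives them no list of their own. The unlisted baseline covariates in the multiple imputation could include vaping, but that would not be adjustment in the outcome model.

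A reader might also infer that the covariate would show whether vaping experience modifies the e-liquid effects. It would not: that needs a pre-specified interaction or subgroup, which is a separate decision.

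**What to change.** In section 29, define recent pre-randomization vaping as the percentage of completed IVR calls from screening to randomization that report any vaping. Pre-specify it as a covariate in all models of vaping-device use, and also in the Week 12 CPD model beside baseline CPD. Describe it as a measure of recent use, not of lifetime experience. State that corrected IVR entries replace the originals, as section 28.1 already does for CPD, and give a rule for participants with no completed call.

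The cost is this wording and one degree of freedom per model. No new data are needed. The change should be made before unblinding, because a covariate added afterwards would be post hoc.
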